7.4.2 Analysis of Secondary Endpoints

1. Change from baseline in IRLS score at each time point
- The measured value and its change from baseline will be summarized using descriptive statistics. Comparison between the placebo group and the gabapentin enacarbil group will be performed using analysis of covariance.
- For the measured value and its change from baseline, the mean ± standard deviation will be plotted.
2. ICGI responder rate at each time point

- The responder rate and its 95% confidence interval will be calculated. Comparison between the placebo group and the gabapentin enacarbil group will be performed using Fisher's exact test.
- The responder rate and its 95% confidence interval will be plotted.

3. PCGI responder rate at each time point

- The responder rate and its 95% confidence interval will be calculated. Comparison between the placebo group and the gabapentin enacarbil group will be performed using Fisher's exact test.
- The responder rate and its 95% confidence interval will be plotted.

4. Change from baseline in Pittsburgh Sleep Quality Index at each time point

- The measured value and its change from baseline will be summarized using descriptive statistics. Comparison between the placebo group and the gabapentin enacarbil group will be performed using analysis of covariance.
- For the measured value and its change from baseline, the mean \pm standard deviation will be plotted.

5. Change from baseline in Athens Insomnia Scale each time point

- The measured value and its change from baseline will be summarized using descriptive statistics. Comparison between the placebo group and the gabapentin enacarbil group will be performed using analysis of covariance.
- For the measured value and its change from baseline, the mean \pm standard deviation will be plotted.

6. Change from baseline in RLS Pain score at each time point

- The measured value and its change from baseline will be summarized using descriptive statistics. Comparison between the placebo group and the gabapentin enacarbil group will be performed using analysis of covariance.
- For the measured value and its change from baseline, the mean \pm standard deviation will be plotted.

7. Change from baseline in EQ-5D-5L at each time point

- The measured value and its change from baseline will be summarized using descriptive statistics.

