#### **3.3 Randomization**

The person responsible for study drug randomization will prepare the treatment codes for randomization of the study drug for the double-blind period, and retain them under lock and key until the time of treatment code breaking.

Stratified allocation will be performed with stratification factors of age ( $< 50$  years and  $\geq 50$  years) at the start of the run-in period and estimated creatinine clearance ( $\geq 60$  to  $< 90$  mL/min and  $\geq 90$  mL/min) at the start of the run-in period, to minimize imbalance in subject characteristics between the treatment groups to allow for proper comparison. The patient registration center will assign the drug numbers to the subjects in accordance with the patient registration procedures.

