## **7.4 Analysis of Efficacy**

### **7.4.1 Analysis of Primary Endpoint**

#### **7.4.1.1 Primary Analysis**

The primary analysis will be performed using the FAS.

The primary efficacy endpoint is the change from baseline in IRLS score at the end of treatment period. Using a repeated measures analysis of variance model, so-called Mixed Model of Repeated Measurements (MMRM) model, having the following average structure, the adjusted mean in each treatment group and its difference (gabapentin enacarbil group - placebo group) at the end of treatment period (Week 12) will be calculated, with comparison between the placebo group and the gabapentin enacarbil group:

Change in IRLS score at each time point

$$= \text{Baseline IRLS score} + \text{Age category}^{\ast 1} + \text{Estimated creatinine clearance category}^{\ast 2} + \\ \text{Treatment group} + \text{Time point} + \text{Treatment group} \times \text{Time point}$$

$\ast^1$  Age category: < 50 years and  $\geq$  50 years

$\ast^2$  Estimated creatinine clearance category:  $\geq$  60 to < 90 mL/min and  $\geq$  90 mL/min

Compound symmetry will be used as the covariance structure for repeated measures of the response variable. A two-sided significance level of 0.05 will be used for statistical tests.

The least-squares mean estimates of the change from baseline in IRLS score at Week 12, the estimates of treatment effect (e.g., least-squares mean change from baseline in IRLS score for gabapentin enacarbil group minus the least-squares mean change from baseline in IRLS score for placebo group) and the corresponding 95% CIs will be reported.

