## **MMRM**

The SAS procedure will be similar to the following:

```
proc mixed;  
  class SUBJECT GROUP VISIT AGE ECC;  
  model CHANGE = GROUP BASE VISIT AGE ECC GROUP*VISIT / ddfm=sat;  
  repeated VISIT /subject = SUBJECT type = cs;
```

```
lsmestimate  
  GROUP*VISIT  
  "GABAPENTIN ENACARBIL v.s. PLACEBO"  
  0 0 ... 0 1 0 0 ... 0 1 / cl alpha=0.05 om;  
  where VISIT in ('Week1', 'Week2', ... , 'Week12');  
run;
```

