**Table 5 Primary, Secondary and Sensitivity Analyses for Primary Endpoint**

Code	Set	Endpoint	Model	Covariates
Primary	FAS	Change from baseline in IRLS score at the end of treatment period (Week 12)	MMRM	Treatment group, Visit, Baseline IRLS score, Age category, Estimated creatinine clearance category, Visit by Treatment group interaction
Secondary	PPS	Change from baseline in IRLS score at the end of treatment period (Week 12)	MMRM	Treatment group, Visit, Baseline IRLS score, Age category, Estimated creatinine clearance category, Visit by Treatment group interaction
S1	FAS	Change from baseline in IRLS score at the end of treatment period (Week 12)	ANCOVA with LOCF	Treatment group, Baseline IRLS score, Age category, Estimated creatinine clearance category
S2	FAS	Change from baseline in IRLS score at the end of treatment period (Week 12)	ANCOVA with MI	Treatment group, Baseline IRLS score, Age category, Estimated creatinine clearance category
S3	FAS	Change from baseline in IRLS score at the end of treatment period (Week 12)	PMM (Last Mean Carried Forward)	Treatment group, Baseline IRLS score, Age category, Estimated creatinine clearance category
S4	FAS	Change from baseline in IRLS score at the end of treatment period (Week 12)	PMM (Last Mean Carried Forward for Gabapentin Enacarbil and Randomized Arm MAR for Placebo)	Treatment group, Baseline IRLS score, Age category, Estimated creatinine clearance category
S5	FAS	Change from baseline in IRLS score at the end of treatment period (Week 12)	PMM (Copy Reference)	Treatment group, Baseline IRLS score, Age category, Estimated creatinine clearance category
S6	FAS	Change from baseline in IRLS score at the end of treatment period (Week 12)	PMM (Jump to Reference)	Treatment group, Baseline IRLS score, Age category, Estimated creatinine clearance category
S7	FAS	Change from baseline in IRLS score at the end of treatment period (Week 12)	PMM (Copy Increment from Reference)	Treatment group, Baseline IRLS score, Age category, Estimated creatinine clearance category

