### **ANCOVA with MI**

The MI ANCOVA model will be used to compare gabapentin enacarbil and placebo group in a fixed sequence procedure:

1. Generate 1000 datasets, using seed 394852, where intermittent missing IRLS score will be imputed for each treatment relying on non-missing data from all subjects within each treatment group using the Monte Carlo Markov Chain (MCMC) imputation model with treatment and the available non-missing IRLS score for each scheduled Week. The MCMC statement in the SAS PROC MI procedure with monotone option will be used. As a result, each dataset will only have missing ending data, or a monotone missing data pattern.
2. For each dataset from step 1, missing ending data (IRLS score up through end of treatment period) will be imputed using seed 394852. As a result, 1000 imputed complete datasets will be generated.
  - Missing data at Week 1 will be imputed using the regression imputation model with the stratification factors, baseline and IRLS score from Week 1, using the SAS PROC MI procedure with the REGRESSION option in the MONOTONE statement.
  - The SAS PROC MI procedure will use data separately from each treatment subjects to impute the missing data for a specific Week (i.e., only those that need the imputation for the Week). Since subjects from the different treatment groups for that Week are excluded from the step, they will not contribute to the imputation for the Week.
  - Repeat for all other scheduled Weeks sequentially (Week 2 to the end of evaluation period). Subjects whose missing data were imputed for previous Weeks will contribute to the imputation for the current Week.

The regression imputation model includes an intercept and the slopes of the IRLS score from previous Weeks and the stratification factors.

3. Analyze each imputed dataset using the ANCOVA using the observed or imputed IRLS score at Week 12. The model will contain terms for baseline IRLS score measurement as a covariate and treatment group and the other stratification factors as fixed effects.
4. Combine estimates from the results of each of the 1000 ANCOVA runs using SAS PROC MIANALYZE.

The least-squares mean estimates of the change from baseline in IRLS score at Week 12, the estimates of treatment effect (e.g., least-squares mean change from baseline in IRLS score for gabapentin enacarbil group minus the least-squares mean change from baseline in IRLS score for placebo group) and the corresponding 95% CIs will be reported.

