### **7.4.2.1 Change from baseline in IRLS score at each time point**

The baseline visit is the measurement at Week 0.

IRLS score and its change from baseline will be summarized by descriptive statistics, by treatment group and visit.

Least square mean difference (gabapentin enacarbil group minus placebo group) of the changes in IRLS score from baseline will be calculated by visit, using ANCOVA model with the baseline value as a covariate. 95% CI and two-sided p-value of the difference will be presented.

Change from baseline in IRLS score will be summarized by subgroups defined in section 7.8.

Following data will be presented graphically by treatment group:

- IRLS score using mean (+/- SD) plot,
- Change in IRLS score from baseline using mean (+/- SD) plot.

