### **7.4.2.4 Change from baseline in Pittsburgh Sleep Quality Index at each time point**

The baseline visit is the measurement at Week 0.

PSQI component scores (sleep quality, sleep latency, sleep duration, habitual sleep efficiency, sleep disturbance, use of sleeping medication, and daytime dysfunction) and PSQI

global score, and their change from baseline will be summarized by descriptive statistics, by treatment group and visit.

Least square mean difference (gabapentin enacarbil group minus placebo group) of the changes in PSQI component and global scores from baseline will be calculated by visit, using the ANCOVA model with the baseline value as a covariate. 95% CI and two-sided p-value of the difference will be presented.

Following data will be presented graphically by treatment group:

- PSQI component scores (sleep quality, sleep latency, sleep duration, habitual sleep efficiency, sleep disturbance, use of sleeping medication, and daytime dysfunction) and PSQI global score using mean (+/- SD) plot,
- Change in PSQI component scores (sleep quality, sleep latency, sleep duration, habitual sleep efficiency, sleep disturbance, use of sleeping medication, and daytime dysfunction) and PSQI global score from baseline using mean (+/- SD) plot.

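### The secondary ANCOVAs (IRLS by visit, PSQI, Athens Insomnia Scale, RLS pain) adjust for baseline only and leave out the two randomisation strata carried by every primary-endpoint model

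*SAP*

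**What the plan says.** SAP 3.3 sets out the randomisation: "Stratified allocation will be performed with stratification factors of age" and estimated creatinine clearance, each in two categories.

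The models for the primary endpoint carry both factors. The MMRM code in SAP 7.4.1.1 reads "model CHANGE = GROUP BASE VISIT AGE ECC GROUP*VISIT / ddfm=sat". SAP Table 5 lists both categories for the primary and per-protocol MMRM, and gives every row from S1 to S7 the covariates "Treatment group, Baseline IRLS score, Age category, Estimated creatinine clearance category". The text for the multiple-imputation ANCOVA (S2) specifies "baseline IRLS score measurement as a covariate and treatment group and the other stratification factors as fixed effects".

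The secondary ANCOVAs are worded differently. IRLS by visit (SAP 7.4.2.1) is analysed "using ANCOVA model with the baseline value as a covariate". PSQI component and global scores (7.4.2.4) are analysed "using the ANCOVA model with the baseline value as a covariate", and the same words recur for the Athens Insomnia Scale (7.4.2.5) and RLS pain (7.4.2.6). None of the four sections mentions age or creatinine clearance.

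Protocol 7.4.2 fixes only the method: "Comparison between the placebo group and the gabapentin enacarbil group will be performed using analysis of covariance". It names no covariates. SAP 7.1 (General Considerations) has no rule that would add the strata to every model, and neither document explains the difference.

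**The concern.** Stratified randomisation removes chance imbalance in the strata from the treatment comparison. A model that omits the strata still leaves their contribution in the residual variance, so its standard error overstates the real sampling error whenever the strata predict outcome. The estimate stays unbiased and the test errs on the safe side, but some precision already paid for by the design is not used.

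Three things make this worth a line in the review:

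- **Reach.** Counting scheduled treatment-period visits, these ANCOVAs produce 41 treatment contrasts. The SAP reports a strata-adjusted estimate for only one of them, IRLS at Week 12, because the primary analysis reports "The least-squares mean estimates of the change from baseline in IRLS score at Week 12" and no other visit. The other 40 have none.
- **Coherence at Week 12.** IRLS change at Week 12 gets a strata-adjusted result from the MMRM and from S1–S7, and a baseline-only result from the by-visit ANCOVA. S1 is also an ANCOVA, so a gap between it and the by-visit result would mix two causes: LOCF versus no imputation, and different covariates.
- **Reproducibility.** A programmer following the four sections literally would fit a different covariate set from the one used elsewhere in the SAP.

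**Working it through.** **1. The plan's own figure.** SAP 4 assumes a difference of 2.56, SD 8.000, two-sided 5% and 80% power, and states 155 per group. The normal approximation is 2 × (1.960 + 0.842)² × 8² / 2.56² = 153.3, so 154. The exact t-test calculation gives 155 (power 80.19%; 154 gives 79.93%). The figure reproduces. With 15% discontinuation, 180 × 0.85 = 153 evaluable per group, which is the number used below.

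**2. Contrasts covered** (visits from SAP 7.10.3.1 and 7.10.3.3).

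| Endpoint | Scores × visits | Contrasts |
|---|---|---|
| IRLS | 1 × 7 (Weeks 1, 2, 4, 6, 8, 10, 12) | 7 |
| PSQI | 8 (7 components + global) × 3 (Weeks 4, 8, 12) | 24 |
| Athens Insomnia Scale | 1 × 3 | 3 |
| RLS pain | 1 × 7 | 7 |
| Total | | 41 |

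Including the end-of-treatment and follow-up analysis visits where defined gives 9 + 32 + 4 + 9 = 54.

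**3. Cost of omitting the strata.** Let R² be the share of baseline-adjusted residual variance that the strata explain. The documents do not give it, so 0, 2, 5 and 10% are assumptions. Write k = √(1 − R²), and d = effect divided by the baseline-only standard error.

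- Excess standard error (and CI width) = 1/k − 1
- True size of a nominal 5% baseline-only test = 2 × [1 − Φ(1.96/k)]
- Extra subjects per arm for the baseline-only model to match the adjusted width = 153 × [1/(1 − R²) − 1]
- Power without strata = Φ((d − 1.96)/k); with strata = Φ(d/k − 1.96)

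For the power rows, d = 1.96 is a contrast with nominal 50% power, where the gain is largest. The second row uses the IRLS planning values, treating 8.000 as the baseline-adjusted residual SD: d = 2.56 / (8 × √(2/153)) = 2.80.

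| Assumed R² | 0 | 2% | 5% | 10% |
|---|---|---|---|---|
| Excess SE / CI width | 0% | 1.0% | 2.6% | 5.4% |
| True size, strata omitted | 5.0% | 4.8% | 4.4% | 3.9% |
| Extra subjects per arm | 0 | 3 | 8 | 17 |
| Power at d = 1.96, without / with | 50.0 / 50.0% | 50.0 / 50.8% | 50.0 / 52.0% | 50.0 / 54.2% |
| Power at planning values, without / with | 79.9 / 79.9% | 80.2 / 80.7% | 80.5 / 81.9% | 81.2 / 83.9% |

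**4. Simulation check.** Block size and stratum shares are not in the documents and were assumed.

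- 306 analysed, equal strata, blocks of 4, 10,000 null runs: at R² = 10% the size was 4.2% without strata and 5.3% with, SE ratio 1.054. At R² = 0 both were about 5.3%.
- 360 randomised, 15% random dropout, stratum shares of 50% (age) and 40% (lower creatinine clearance), blocks of 2, 4 and 8, 9,000 runs per cell: at R² = 10% the size was 3.9 to 4.1% without and 4.8 to 5.1% with, SE excess 5.4%. At R² = 0 the two models were equivalent.

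Both simulations agree with the formulas.

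**5. Price of adding the strata when they explain nothing.** With 306 subjects the residual degrees of freedom go from 303 to 301 and the critical t from 1.9678 to 1.9679. Power falls by less than 0.01 points.

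**The case against.** The strongest reply is that nothing here is an error. Baseline-only ANCOVA is a legitimate prespecified choice, it is compatible with the protocol, and it errs conservatively. The documents set no testing order or alpha allocation for secondary endpoints, so a slightly wide interval changes no decision rule. All of that stands, and it is why the point is minor.

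The wording may also be shorthand. The four sections do not name treatment group as a model term either, yet it must be there to yield a difference in least-squares means. The S2 text reserves the word covariate for baseline and lists treatment and strata separately as fixed effects, so the secondary sentences could be a shortened form of the same model. That reading is possible. But nothing in SAP 7.1 supplies the missing terms, and S2 shows that the SAP names the strata where it wants them. Either reading calls for the same edit.

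The size is also uncertain. If one evenly split factor carried all of R² = 10%, its two categories would differ by 2 × √0.10 = 0.63 SD, about 5 IRLS points at SD 8, or roughly twice the planned effect of 2.56. Nothing in the documents supports a gap that large, so the left half of the table is the more cautious guide.

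The contrast count should not be over-read. Of the 41, 21 are PSQI component scores (7 × 3), and 6 are IRLS visits before Week 12, which the primary MMRM already fits with the strata although it is not specified to report them. Nor would the edit remove every difference: the Week 12 ANCOVA and the MMRM would still handle missing data differently, and the ICGI and PCGI comparisons would remain unadjusted.

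**Conclusion.** The point holds and is minor. The four secondary ANCOVAs name only the baseline value, while the primary, per-protocol and S1–S7 models all carry the factors used to randomise. No reason is given.

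If the models are run as written, the results are valid. There is no bias and no inflation of type I error, and the primary analysis is untouched. The loss is a modest excess in interval width, from nothing to 5.4%, and between 0 and 4.2 points of power depending on the contrast. This rests on an assumed R² of 0 to 10%. The true value is not in the documents and may be zero, in which case nothing is lost. The text, by contrast, needs no assumption: the covariate sets differ.

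**What to change.** Before unblinding, add age category (<50, ≥50 years) and estimated creatinine clearance category (60 to <90, ≥90 mL/min) as fixed effects to the ANCOVAs in SAP 7.4.2.1, 7.4.2.4, 7.4.2.5 and 7.4.2.6. If they were always intended, say so in those sections. If they were left out on purpose, give the reason.

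The cost is a line of wording in each section. Both variables are already collected and categorised (SAP Table 3) and used in the primary model. Two degrees of freedom are spent, with negligible effect. Protocol 7.4.2 names no covariates, so no amendment is needed. Keep the protocol-specified Fisher's exact tests for ICGI and PCGI.

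Separately, optional and descriptive only: SAP Table 6 does not list the creatinine clearance category as a subgroup factor. It could be added for IRLS change and TEAEs, because the Week 1 active regimen differs by that stratum (Protocol 5.1.2). The separate TLF specifications may already cover this, and the main point does not depend on it.

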### **7.4.2.2 ICGI responder rate at each time point**

The ICGI responder rate will be presented by treatment group. 95% CIs of the responder rate will be calculated using Clopper-Pearson method.

Difference (gabapentin enacarbil group minus placebo group) of the ICGI responder rates and its 95% CI (normal approximation with continuity correction) will be calculated. The two treatment groups will be compared using Fisher's exact test.

Following data will be presented graphically by treatment group:

- ICGI responder rate (+/- 95% CI) plot.

### **7.4.2.3 PCGI responder rate at each time point**

The PCGI responder rate will be presented by treatment group. 95% CIs of the responder rate will be calculated using Clopper-Pearson method.

Difference (gabapentin enacarbil group minus placebo group) of the PCGI responder rates and its 95% CI (normal approximation with continuity correction) will be calculated. The two treatment groups will be compared using Fisher's exact test.

Following data will be presented graphically by treatment group:

- PCGI responder rate (+/- 95% CI) plot.

### **7.4.2.4 Change from baseline in Pittsburgh Sleep Quality Index at each time point**

The baseline visit is the measurement at Week 0.

PSQI component scores (sleep quality, sleep latency, sleep duration, habitual sleep efficiency, sleep disturbance, use of sleeping medication, and daytime dysfunction) and PSQI

global score, and their change from baseline will be summarized by descriptive statistics, by treatment group and visit.

Least square mean difference (gabapentin enacarbil group minus placebo group) of the changes in PSQI component and global scores from baseline will be calculated by visit, using the ANCOVA model with the baseline value as a covariate. 95% CI and two-sided p-value of the difference will be presented.

Following data will be presented graphically by treatment group:

- PSQI component scores (sleep quality, sleep latency, sleep duration, habitual sleep efficiency, sleep disturbance, use of sleeping medication, and daytime dysfunction) and PSQI global score using mean (+/- SD) plot,
- Change in PSQI component scores (sleep quality, sleep latency, sleep duration, habitual sleep efficiency, sleep disturbance, use of sleeping medication, and daytime dysfunction) and PSQI global score from baseline using mean (+/- SD) plot.

#### **7.4.2.5 Change from baseline in Athens Insomnia Scale at each time point**

The baseline visit is the measurement at Week 0.

Total score of Athens insomnia scale and its change from baseline will be summarized by descriptive statistics, by treatment group and visit.

Least square mean difference (gabapentin enacarbil group minus placebo group) of the changes in total score of Athens insomnia scale from baseline will be calculated by visit, using the ANCOVA model with the baseline value as a covariate. 95% CI and two-sided p-value of the difference will be presented.

Following data will be presented graphically by treatment group:

- Total score of Athens insomnia scale using mean (+/- SD) plot,
- Change in total score of Athens insomnia scale from baseline using mean (+/- SD) plot.

